1.5 Secondary Outcomes

The secondary outcome measures will be the change in heart rate, blood pressure, and subjective arousal from baseline for each stimulation location and participant group.

2.1 Pre-study surveys

Prior to the first visit, participants will complete five clinically validated surveys:

- 1 The American Urological Association Symptom Index (AUASI) bladder symptom index [19]
- 2 The Female Sexual Function Index (FSFI) [20]
- 3 Fecal Incontinence Severity Index (FISI) [21]
- 4 Patient Assessment of Constipation-Symptoms (PAC-SYM) [22]
- 5 The short-form (SF-36) quality of life survey [23], [24]

Surveys will be completed over the phone or online in REDCap, a standard clinical tool for survey data collection [25]. Each survey is included in section 29.1.

2.2 Study visits 1 & 2

The same steps will be followed for all three Aims. Participants will have two study visits. The interval between visits will be at least one month but not more than five months.

On each study day, subjects will complete a urine pregnancy test. Next, subjects will recline in a comfortable position on an elevated table, with pillows and blankets provided if desired. An MCRU staff member will be available to provide assistance, if needed, in addition to one or more clinical research team members. A vaginal plethysmography transducer (Biopac TSD204) will be inserted about 3 inches into the patient's vagina by a clinical staff member or by the patient with clinician supervision. The transducer measures vaginal pulse amplitude (VPA), the standard clinical technique for assessing genital sexual arousal in women [5], [26]–[28]. No energy is transmitted from the TSD204 to the participant. A heart rate monitor (e.g. electrocardiogram or pulse oximetry) and blood pressure monitor will be placed on the participant's arm, hand, or chest (as is appropriate per monitor) to monitor off-target autonomic responses.

On the first study day, one of the two stimulation approaches will be randomly selected and prepared. For dorsal genital nerve stimulation, two circular 1.25-inch diameter transcutaneous electrical stimulation (TENS)

[figure not shown]

Figure 1. Electrode locations (red dots) for genital nerve stimulation, on either side of the clitoris.

electrodes (ValuTrode Fabric CF3200 or equivalent) will be placed on either lateral side of the clitoris (Figure 1). For tibial nerve stimulation, the two electrodes will be placed just above the medial malleolus and the ipsilateral calcaneus on one leg (Figure 2). The placement of TENS device will be performed by clinical study team members, specifically [name], [name], or other clinical practitioners or fellows who are study team members. Each clinical study team member is a practicing MD physician trained in the use of neuromodulation including technology such as this. The conductivity of the electrodes may be tested with an impedance meter (Digitimer D175), which is connected to an electrode set and uses very low, imperceptible current levels. If the meter indicates poor conductivity, the electrodes may be repositioned.

[figure not shown]

Figure 2. Electrode locations (white circles) for tibial nerve stimulation near the ankle.

Prior to starting stimulation with a TENS device (Empi Select, or similar), the stimulation amplitude will be determined. The current will be increased until the participant expresses discomfort and then reduced to a comfortable level, or a maximum level of 60 mA is reached. During stimulation, the set stimulation amplitude will be applied at a frequency of 20 Hz, which is standard for PTNS and the frequency we used in our previous human subjects' study (HUM00101713).

Participants will be shown a neutral video (nature film excerpt) and an erotic film clip featuring sexually explicit material at different intervals of the testing period. The use of videos in this manner is a standard method in studies of sexual function [16]–[18], and may help enhance an arousal response. Two videos will be loaded on a laptop computer in a fixed order that will not require patient intervention. Participants will choose a video based on their preference in viewing either two women or a woman and a man engaging in sexual activities.

As shown in Figure 4, during the testing period participants will first view a 5-minute neutral film depicting nature scenes to allow blood flow levels to stabilize. This will be followed by a 10-minute period while the subject watches an erotic film clip for assessment of arousal responses without electrical stimulation. The erotic film clip depicts sexually explicit material of two consenting adults engaging in sexual activities including manual and oral stimulation of breasts and genitals as well as penile-vaginal intercourse depending on the film chosen. A 10-minute clip of the same neutral film will follow, to allow blood flow levels to return to baseline. Five minutes into this film, electrical stimulation will be resumed at the previously determined amplitude. Finally, the subject will view another 10-minute erotic film clip depicting similar sexually explicit material as the first while electrical stimulation remains on as the last sequence in the testing.

At the beginning of the VPA recording sequence, in between each video transition, and at the end of the VPA recording sequence (a total of 5 times), participants will view a 15-30-second screen prompt asking them to record their agreement with the statement, “I feel sexually aroused (e.g. sexually excited, turned on) right now,” according to a 5-point Likert scale: (1) *strongly disagree*, (2) *disagree*, (3) *neutral*, (4) *agree*, and (5) *strongly agree*. At the end of each session participants will be asked their general opinions of that stimulation session, whether it seemed to elicit any genital arousal responses such as lubrication, warmth, tingling, or any

sensations they would characterize as pleasurable, and whether they would consider further use of it.

At the second study day, stimulation using the same steps will be performed at the other location.

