1.3 Specific Aims

The aims of this study are to:

- Aim 1: Compare the effect of skin-surface genital nerve stimulation and tibial nerve stimulation on vaginal blood flow in women with spinal cord injury caused neurogenic sexual dysfunction.
- Aim 2: Compare the effect of skin-surface genital nerve stimulation and tibial nerve stimulation on vaginal blood flow in women with non-neurogenic female sexual dysfunction.
- Aim 3: Compare the effect of skin-surface genital nerve stimulation and tibial nerve stimulation on vaginal blood flow in neurologically-intact women without sexual dysfunction.

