3.1 Sample size

The target population size (N=40) is based on intended recruitment of 40 women; 10 normal women (e.g. without SCI nor FSD), 10 non-SCI women with FSD, and 20 women with SCI. Efforts will be made to recruit equal numbers between AIS A SCI and AIS B-C SCI participants, but it may be challenging to get exactly 10 in each SCI group. The AIS A SCI and AIS B-C SCI is based on the International Standards for Neurological Classification of Spinal Cord Injury. AIS A SCI refers to complete, no sensory or motor function SCI, while AIS B-C SCI refers to incomplete SCI (e.g. sensory but not motor function is preserved). This is a pilot study with no comparable studies for identifying an effect size and performing a power analysis. If we determine that a larger population size is needed for any participant groups, based on preliminary data analyses, then the target group size will be increased.

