3.2 Data Analysis plan

VPA will undergo optimization, filtration, and a spectral analysis as in [11], [12], [15]. The change in VPA from the average baseline value will be determined for each stimulation at four-minute intervals, during which stimulation is paused for ten seconds. Although VPA will be recorded continuously, the genital nerve stimulation may cause a motion artifact and so equal pauses in stimuli will be used in each interval for both stimulation approaches. We may eliminate this pause if data analysis indicates that there are no artifacts or that filtration and spectral analysis eliminates artifacts. Similar calculations may be done for the heart rate and blood pressure. An ANOVA will be performed to determine whether participant type, stimulation location, and stimulation interval (i.e. timing within stimulation duration) has an effect on VPA. Wilcoxon signed rank tests will be used to test for differences within the groups. Similarly, changes in cardiovascular parameters will be assessed, to see if general autonomic responses are triggered with either stimulation location or patient group. We will also look for correlations between the pre-session survey scores (e.g. FSFI total score), patient demographics (e.g. age,

BMI), and changes in items (e.g. decrease in incontinence events) with the maximal VPA responses with a regression analysis.

4. Study Recruitment

This study addresses a potentially sensitive topic. During the recruitment and consenting processes, all study activities will be carefully explained with particular attention to matters of privacy and confidentiality. Many women with spinal cord injury (SCI) have had negative healthcare experiences with respect to reproductive health. Alternatively, grateful patients can feel compelled to participate out of a sense of loyalty. As such, for recruitment and consenting processes, we will emphasize that participation is entirely voluntary, and refusal or withdrawal will have no effect on any care they receive.

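### No balancing of site order within participant group is described and no visit term is planned, so a chance order imbalance would carry part of any visit effect into the genital-versus-tibial contrast

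*Combined protocol and SAP*

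**What the plan says.** Each Aim in section 1.3 is a within-group comparison of the two sites. Aim 2, for example, is to "Compare the effect of skin-surface genital nerve stimulation and tibial nerve stimulation on vaginal blood flow in women with non-neurogenic female sexual dysfunction"; Aims 1 and 3 are parallel for women with SCI and women without dysfunction.

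The design in section 2.2 is a two-visit crossover. On allocation it says "On the first study day, one of the two stimulation approaches will be randomly selected and prepared", and then "At the second study day, stimulation using the same steps will be performed at the other location". On spacing: "The interval between visits will be at least one month but not more than five months". No ratio, list, block, stratum or concealment is described.

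Section 3.1 plans "10 normal women (e.g. without SCI nor FSD), 10 non-SCI women with FSD, and 20 women with SCI". It hopes for equal numbers of AIS A and AIS B-C women but concedes that "it may be challenging to get exactly 10 in each SCI group".

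For the analysis, section 3.2 states: "An ANOVA will be performed to determine whether participant type, stimulation location, and stimulation interval" (the last meaning time within stimulation) affect VPA. It adds: "Wilcoxon signed rank tests will be used to test for differences within the groups". Section 1.4 names the same three ANOVA factors. Neither section includes visit or order.

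**The concern.** In a two-visit crossover, site and visit separate cleanly only if the two orders are equally common or the analysis adjusts for visit. The plan secures neither.

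A visit effect is plausible, though this is an assumption. Visit 2 repeats the same procedure, with the same probe and the same kind of film, in a woman who now knows the session. Stimulation stays on through the second erotic clip, so the primary outcome can include a film response that familiarity might change.

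If more women in one group happen to receive genital stimulation first, part of that change would read as a site difference. Section 1.2 intends to compare effects between groups to learn about mechanism. Different order splits in different groups could then look like a site preference specific to one type of participant.

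**Working it through.** **Inputs from the documents.** Aim 1: n = 20. Aim 2: n = 10. Aim 3: n = 10. These add to the stated 40. That total is a recruitment target without alpha, SD or effect size, so there is no power figure to reproduce.

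**Assumptions.** Independent 50:50 selection for each woman, and complete data at both visits. The visit effect is left unspecified except in step 4.

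**1. Share of the visit effect in the site contrast.** Let τ be the true genital-minus-tibial difference and π the visit-2-minus-visit-1 effect. A woman with genital first has expected difference τ − π; with tibial first, τ + π. If k of n have genital first, the unadjusted mean difference is τ + π(n − 2k)/n. The absolute share |n − 2k|/n is 0.2 at 6:4, 0.4 at 7:3 or 14:6, and 0.6 at 8:2 or 16:4.

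**2. Probability of each split,** with k ~ Binomial(n, 0.5).

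| Group | Split | Calculation | Probability |
|---|---|---|---|
| n = 10 | exactly 5:5 | 252/1024 | 24.6% |
| n = 10 | 7:3 or worse | 2 × (120 + 45 + 10 + 1)/1024 | 34.4% |
| n = 10 | 8:2 or worse | 2 × (45 + 10 + 1)/1024 | 10.9% |
| n = 20 | exactly 10:10 | 184,756/1,048,576 | 17.6% |
| n = 20 | 14:6 or worse | 2 × 60,460/1,048,576 | 11.5% |
| n = 20 | 16:4 or worse | binomial tail | 1.2% |

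Across the three Aim groups:
- At least one with a share of 40% or more: 1 − (1 − 0.344)² × (1 − 0.115) = 61.9%.
- At least one with a share of 60% or more: 1 − (1 − 0.109)² × (1 − 0.012) ≈ 22%.
- All three exactly balanced: 0.246² × 0.176 = 1.1%.

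**3. Averaged over randomisations.** The expectation of (n − 2k)/n is 0, so the contrast is unbiased. Its mean square is 1/n, so simple selection adds π²/n to the variance of the unadjusted contrast. The root mean square share is 1/√10 = 0.32 at n = 10 and 1/√20 = 0.22 at n = 20.

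**4. False-positive rate of an unadjusted site-versus-site signed-rank test.** Simulation with 40,000 runs, no site effect, normal differences and two-sided 5%. The visit effect is in SDs of the within-woman difference, and its values are assumed.

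| Visit effect (n = 10) | 5:5 | 6:4 | 7:3 | 8:2 | 9:1 |
|---|---|---|---|---|---|
| 0.25 SD | 4.3% | 4.5% | 5.2% | 6.5% | 8.2% |
| 0.5 SD | 2.9% | 3.5% | 5.9% | 10.2% | 17.1% |
| 1.0 SD | 0.7% | 1.4% | 6.0% | 18.7% | 45.2% |

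At n = 20 and 14:6 the rate is 9.4% at 0.5 SD and 15.9% at 1.0 SD. Averaged over simple selection, it stays between 4.7% and 5.2% throughout. At an equal split the test is conservative, because the visit effect remains as spread in the differences.

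**5. Adjusting for visit without balancing.** With complete data, the adjusted estimate is the average of the two order-specific means. Its variance relative to an equal split is n²/(4k(n − k)): 100/84 = 1.19 at 7:3 and 100/64 = 1.56 at 8:2. Adjustment removes the mean visit effect whenever both orders are present, but an unequal split costs precision.

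**The case against.** Several points on the other side have force.

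- *The method is not stated.* A reader might infer that each woman's order is picked independently with no balancing. The documents do not say that; a balanced list would also fit their wording. Every probability above is therefore conditional on simple selection. If blocking is already intended, writing it down settles the design half of the point.
- *Aim 1 has 20 women.* A reader might treat the study as four groups of 10, which gives 81% for at least one split of 7:3 or worse. The AIS subgroups are a recruitment intention, and no Aim or test is tied to them. The figure that matches the Aims is 62%.
- *Random order protects against bias.* A reader might call the site contrast biased or the test invalid. Neither holds averaged over randomisations, as steps 3 and 4 show. But the trial is run once, and its reported contrasts depend on the split obtained.
- *The visit effect may be small.* Its size is not given, and visits are one to five months apart. The outcome is a change from mean baseline, so a shift common to baseline and response cancels. A change in responsiveness would not. Each session also records an erotic clip without stimulation, but the plan does not commit to using it as a comparator.
- *The signed-rank tests may not compare sites.* Section 3.2 says only that they address within-group differences, so stimulation against baseline is possible. The ANOVA can take a visit term; the plan simply omits it.
- *This is a pilot.* That limits the consequences, but simple selection balances worst in small groups.

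**Conclusion.** The point holds in a limited form. The documents describe no balancing of order and plan no adjustment for visit, so an order imbalance would pass into the site contrast. Under simple 50:50 selection, the chance that at least 40% of any visit effect enters is 34% in each of Aims 2 and 3, 11.5% in Aim 1, and 62% for at least one of the three. Some imbalance in at least one Aim is almost certain (98.9%), but most splits in a single group are milder than 7:3.

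This is chance confounding in the realised split plus added variance. The documents do not support a claim of systematic bias or of an inflated overall error rate. The consequence scales with a visit effect that they do not quantify; if it is near zero, little is lost. The change is worth making because it is cheap and improves both balance and precision.

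**What to change.** **Section 2.2.** Assign order (genital first or tibial first) 1:1 from a pre-generated, concealed list in permuted blocks of varying size (2 or 4), stratified by participant group (no dysfunction, non-SCI FSD, AIS A, AIS B-C). Release each assignment at visit 1. REDCap, already in use, could hold the list. A stratum that stops inside a block differs by at most 2, so a group of 10 is 6:4 at worst (share 0.2). Two SCI strata each off by 2 give at worst 12:8 (share 4/20 = 0.2). The list can be extended if group sizes are raised under section 3.1.

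**Section 3.2.** Add visit (period) to the model, with participant as a random effect. For any site-versus-site rank test, use a period-adjusted version that compares the visit differences between the two orders. This is needed even with blocking, because dropout can reopen an imbalance and the unadjusted signed-rank test is conservative at an equal split when a visit effect exists.

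**Cost.** One paragraph in each section and one list; no extra participants, visits or procedures. The downsides are slight predictability at block ends, limited by varying block size, and one degree of freedom for the visit term.

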1.2 Objective

The overall purpose of this research is to improve sexual function in women with sexual dysfunction. The goal of this study is to see if either of two nerve stimulation interventions cause a short-term change in vaginal blood flow. The effect of this intervention will be compared between women who have neurogenic (spinal cord injury) or non-neurogenic dysfunction and healthy women, to reveal mechanisms underlying neural control over vaginal blood flow.

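### In the erotic-film blocks, stimulation on versus off is aliased with clip content as well as order; this limits the Section 1.2 goal, not the genital-versus-tibial comparison

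*Combined protocol and SAP*

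**What the plan says.** Section 2.2 describes one film sequence for all three Aims. After five minutes of neutral film comes "an erotic film clip for assessment of arousal responses without electrical stimulation", lasting ten minutes. A ten-minute clip of the same neutral film follows: "Five minutes into this film, electrical stimulation will be resumed at the previously determined amplitude". The session closes with a second, different erotic clip of equal length and like content, shown "while electrical stimulation remains on as the last sequence in the testing".

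On the films, Section 2.2 adds: "Two videos will be loaded on a laptop computer in a fixed order that will not require patient intervention". It also says: "Participants will choose a video based on their preference in viewing either two women or a woman and a man engaging in sexual activities". It does not say whether that choice carries over to visit 2.

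The second visit repeats the procedure at the other site. The only randomisation described is which site is used first. No counterbalancing of clips and no session without stimulation is described.

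Section 1.2 gives the goal as "to see if either of two nerve stimulation interventions cause a short-term change in vaginal blood flow". Aims 1-3 (Section 1.3) compare genital with tibial stimulation within each participant group. The primary outcome (Section 1.4) is the largest VPA change from a mean baseline, by site and group. The ANOVA (Section 3.2) has factors for group, site and time interval, and none for clip, block order or visit. Wilcoxon signed-rank tests are planned within groups, without naming the pairs to be compared.

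**The concern.** The unstimulated erotic clip is the natural within-session reference for the stimulated one. The two blocks differ in three ways at once: stimulation, position in the session, and the clip itself. If the second clip is somewhat more arousing, VPA would rise in the last block in every group and at both sites, and the rise would look like a stimulation effect. If it is less arousing, a real effect would be hidden. The clips are called similar, but no matching or pre-rating for arousal is described, so the size of the difference cannot be checked.

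The film category raises a smaller matter: a woman could choose differently at her second visit.

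**Working it through.** **Inputs.** From Section 3.1: 10 + 10 + 20 = 40 women. From Section 2.2: two visits, two erotic blocks per visit, stimulation always in the second block. The plan has no power calculation, effect size, SD or significance level to reproduce. A two-sided 5% level and the sizes of the clip shift below are assumptions.

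**Step 1: what can be estimated.** Take the 40 x 2 x 2 erotic-block readings and fit 40 participant intercepts plus visit, genital-on, tibial-on, block order and clip: 40 + 5 = 45 columns. Under the described sequence there are two exact dependencies:
- clip = block order
- genital-on + tibial-on = block order

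The rank is 45 - 2 = 43. Genital-on, tibial-on, order and clip are each non-estimable. Genital minus tibial is estimable.

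**Step 2: which contrasts are affected.** Let the stimulation effects be τG and τT, the order effect ω, and the clip difference (second minus first) κ. The expected on-off differences are:
- genital visit: DG = τG + ω + κ
- tibial visit: DT = τT + ω + κ
- site comparison: DG - DT = τG - τT

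The on-off contrast carries ω + κ. The site comparison does not, provided the shift is the same at both visits.

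**Step 3: illustrative size.** Set τ = 0 and ω = 0, and let d be κ divided by the SD of the paired on-off difference. The rejection rate is P(|T| > t(0.975, n-1)), where T is noncentral t with n-1 degrees of freedom and noncentrality d√n. For example, n = 10 and d = 0.5 give noncentrality 0.5 × √10 = 1.58 and a rate of 0.293.

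| n | d = 0.2 | d = 0.3 | d = 0.5 |
|---|---|---|---|
| 10 | 0.088 | 0.136 | 0.293 |
| 20 | 0.136 | 0.247 | 0.565 |
| 40 | 0.235 | 0.457 | 0.869 |

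Simulated signed-rank tests (4,000 runs each) agree: at d = 0.5 they reject in 28%, 55% and 85% of runs for n = 10, 20 and 40. The simulated genital-versus-tibial test stays at 4-6% for every shift tried, from 0 to 0.8 SD.

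The opposite sign masks. With a true effect of 0.5 SD and κ = -0.5 SD, the expected on-off difference is 0.5 - 0.5 = 0.

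**Step 4: what swapping clips achieves.** With clip order balanced, half the women have expected difference τ + ω + κ and half τ + ω - κ, which average to τ + ω. The rank rises to 44 of 45: clip becomes estimable, while stimulation remains aliased with order. Separating order too would need more. Reversing the on-off blocks as well gives 45 of 45, but only if stimulation does not carry over into a later unstimulated block. Adding a session of the same films without stimulation gives 44 of 45; both site effects become estimable, and order and clip stay joined.

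**The case against.** **The Aims compare sites.** A reader might infer that the genital-versus-tibial comparison is biased too. The documents do not support that: both visits use the same sequence, the first site is chosen at random, and a common shift cancels. What remains is the Section 1.2 goal. Equal responses at the two sites cannot tell two working sites from two inert ones.

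**Not every reading is on an erotic clip.** The neutral film has unstimulated and stimulated periods, so it offers an off-on contrast free of erotic-clip content. That stands. It still carries order and recovery from the first erotic clip.

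**The rejection rates are not the plan's error rates.** A reader might take them as such. The plan names no test of second against first clip and gives no shift, so they show sensitivity only.

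**The fixed-clip reading is partly an inference.** The sentence on two videos may mean the neutral and erotic pair, and Figure 4 is not available in the text read here. But the last block is plainly a second erotic clip, and no swapping is described.

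**A film change at visit 2.** It is tempting to call this a bias in the site comparison. Because site order is random, a change is not systematically tied to either site and mainly adds noise.

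**It is a pilot.** True, but counterbalancing clips needs no more women or visits.

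**Conclusion.** The point holds for the on-off contrast in the erotic blocks: as described, stimulation, order and clip cannot be separated by any analysis of those blocks. It bears on the causal goal of Section 1.2 and leaves the site comparison of Aims 1-3 interpretable.

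The size is unknown. Under an assumed clip shift of 0.2 to 0.5 SD and an assumed two-sided 5% paired test, false rejection runs from 9% (n=10, smallest shift) to 87% (n=40, largest shift); a shift the other way hides an effect. This assumes that one clip always fills each slot, which is the natural reading of Section 2.2. Swapping clips removes the clip component only, so it would be wrong to infer that it makes the on-off contrast fully causal. The change is worth making because it is cheap and removes one of the two confounders.

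**What to change.** - Within each film category, randomise which of the two erotic clips is shown first, balanced within participant group.
- Keep each woman's film category and clip order the same at both visits. This mainly avoids added noise in the site comparison.
- Name the on-off contrast in Section 3.2 and analyse it in a model with a clip-order term; a signed-rank test cannot carry one.
- State that this contrast still includes an order effect. A claim that stimulation itself caused the change must then be qualified, while the site difference can be interpreted as planned.

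The cost is one extra playlist per film category (four in place of two) and one model degree of freedom, for example 9 to 8 in a within-group analysis of 10 women. Stimulation, visits and sample size do not change.
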